#### **7.4.8. Assessment of Intensity**

An event is defined as “serious” when it meets at least one of the predefined outcomes as described in the definition of an SAE ([Section 7.4.2](#)), NOT when it is rated as severe.

The severity (or intensity) of an AR or AE refers to the extent to which it affects the participant’s daily activities. The Toxicity Grading Scale for Healthy Adult and Adolescent Volunteers Enrolled in Preventive Vaccine Clinical Trials ([DHHS 2007](#)) will be used to categorize local and systemic reactogenicity events (solicited ARs), clinical laboratory test results, and vital sign measurements observed during this study. Specific criteria for local and systemic reactogenicity events are presented in [Section 7.4.3](#).

The determination of severity for all unsolicited AEs should be made by the investigator based upon medical judgment and the definitions of severity as follows:

- Mild: These events do not interfere with the participant's daily activities.
- Moderate: These events cause some interference with the participant's daily activities and require limited or no medical intervention.
- Severe: These events prevent the participant's daily activity and require intensive therapeutic intervention.

Study staff should elicit from the participant the impact of AEs on the participant's activities of daily living to assess severity and document appropriately in the participant's source documentation. Changes in the severity of an AE should be documented in the participant's source documentation to allow an assessment of the duration of the event at each level of intensity to be performed. An AE characterized as intermittent requires documentation of onset and duration of each episode. An AE that fluctuates in severity during the course of the event is reported once in the eCRF at the highest severity observed.

#### **7.4.9. Assessment of Causality**

The investigator's assessment of an AE's relationship to IP is part of the documentation process but is not a factor in determining what is or is not reported in the study.

The investigator will assess causality (ie, whether there is a reasonable possibility that the IP caused the event) for all AEs and SAEs. The relationship will be characterized using the following classification:

**Not related:** There is not a reasonable possibility of a relationship to the IP. Participant did not receive the IP OR temporal sequence of the AE onset relative to administration of the IP is not reasonable OR the AE is more likely explained by another cause than the IP.

**Related:** There is a reasonable possibility of a relationship to the IP. There is evidence of exposure to the IP. The temporal sequence of the AE onset relative to the administration of the IP is reasonable. The AE is more likely explained by the IP than by another cause.

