#### **Events NOT Meeting the Adverse Event Definition**

- Procedures planned before study entry (eg, hospitalization for preplanned surgical procedure).
- Medical or surgical procedure (eg, endoscopy, appendectomy): the condition that leads to the procedure should be the AE.
- Situations in which an untoward medical occurrence did not occur (social and/or convenience admission to a hospital).

An AR is any AE for which there is a reasonable possibility that the vaccine caused the AE ([Section 7.4.3](#)). For the purposes of investigational new drug safety reporting, “reasonable possibility” means that there is evidence to suggest a causal relationship between the vaccine and the AE.

An unsolicited AE is any AE reported by the participant that is not specified as a solicited AR in the protocol or is specified as a solicited AR but starts outside the protocol-defined period for reporting solicited ARs (ie, 7 days after vaccination).

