#### **7.4.11. Reporting SAEs**

Prompt notification by the investigator to the Sponsor of an SAE is essential so that legal obligations and ethical responsibilities toward the safety of participants and the safety of a study intervention under clinical investigation are met.

Any AE considered serious by the investigator or that meets SAE criteria ([Section 7.4.2](#)) must be reported to the Sponsor immediately (within 24 hours of becoming aware of the SAE) via the EDC system. The investigator will assess whether there is a reasonable possibility that the IP caused the SAE. The Sponsor will be responsible for notifying the relevant regulatory authorities of any SAE as outlined in 21 US CFR Parts 312 and 320. The investigator is responsible for notifying the institutional review board (IRB) directly.

If the eCRF is unavailable at the time of the SAE, the following contact information is to be used for SAE reporting:

- SAE Mailbox: Safety\[contact]
- SAE Hotline (USA and Canada): [contact]
- SAE Fax Line (USA and Canada): [contact]

Regulatory reporting requirements for SAEs are described in [Section 7.4.15](#).

The investigator and any qualified designees are responsible for detecting, documenting, and recording events that meet the definition of an AE, including SAEs, and remain responsible for following up AEs that are serious, considered related to IP or study procedures, or that caused the participant to discontinue the study.

Any SAE occurring after the EoS and considered to be caused by the study vaccine must be reported to the Sponsor.

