#### **6.3.1.1. Incidence of Adverse Events**

An overall summary of unsolicited TEAEs including the number and percentage of subjects who experience the following will be presented:

- Any unsolicited TEAEs
- Any serious TEAEs
- Any fatal TEAEs
- Any unsolicited MAAEs
- Any unsolicited TEAEs leading to discontinuation from participation in the study
- Any unsolicited severe TEAEs
- Any unsolicited AESIs

The same table will also include number and percentage of subjects with unsolicited TEAEs that are treatment-related per PI's assessment in each of the above categories.

The above overall summaries will be done for unsolicited non-serious TEAEs with applicable TEAE categories.

In addition, Unsolicited AEs, unsolicited TEAEs leading to discontinuation from the study, serious AEs, unsolicited MAAEs, and AESIs, will be listed. AESI other than myocarditis and pericarditis; AESI of myocarditis and pericarditis, will be provided separately.

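### Protocol 7.4.9 states two conflicting causality thresholds, so an unsolicited AE that the vaccine could reasonably have caused, but that has a likelier alternative, satisfies text in both Related and Not related

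*Protocol*

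**What the plan says.** Protocol 7.4.9 puts the causality question as "whether there is a reasonable possibility that the IP caused the event". It offers two categories, Related and Not related, with no third category and no rule for ties. Each opens with a sentence affirming or denying a reasonable possibility of a relationship to the IP, and each continues with further text:

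- **Not related** lists three conditions joined by OR: no IP received, unreasonable timing, or that "the AE is more likely explained by another cause than the IP".
- **Related** adds statements on exposure and timing, and ends with "The AE is more likely explained by the IP than by another cause".

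The same standard appears elsewhere without any comparison. In 7.4.1, "An AR is any AE for which there is a reasonable possibility that the vaccine caused the AE". For investigational new drug safety reporting, that section adds that a reasonable possibility "means that there is evidence to suggest a causal relationship between the vaccine and the AE". For SAEs, 7.4.11 says: "The investigator will assess whether there is a reasonable possibility that the IP caused the SAE".

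The SAP has no causality definition of its own. SAP 6.3.1.1 reports the "number and percentage of subjects with unsolicited TEAEs that are treatment-related per PI's assessment", and SAP 6.3.1.2 tabulates treatment-related events by system organ class and preferred term. Protocol Table 7 has rows for treatment-related unsolicited AEs, SAEs and severe unsolicited AEs.

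**The concern.** A reasonable possibility and a likelier-than-the-alternative test are different thresholds. An event can have real evidence pointing to the vaccine and still have a more probable explanation. Section 7.4.9 treats that event as related under one sentence and as not related under another.

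The classification supplies every treatment-related row in the safety tables. It also bears on two duties that apply once participation has ended: 7.4.11 (SAEs after the end of study thought to be caused by the vaccine) and 7.4.12 (SAEs learned of after withdrawal or completion and thought reasonably related). If investigators at up to 13 sites resolve the conflict differently, those counts depend partly on which sentence each one applied. Plausible alternatives are to be expected: protocol 3.2 anticipates circulating SARS-CoV-2, and 7.3.6 notes that COVID-19 symptoms overlap with vaccine reactions.

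**Working it through.** The plan gives no figure to reproduce, so the check is an enumeration.

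**Set-up.** Take an unsolicited AE after receipt of IP, with reasonable timing and a reasonable possibility that the IP caused it. The exposure and timing text is then satisfied, and only the comparison with another cause varies.

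| Weight of IP against the other cause | Reasonable-possibility sentence | Comparative text |
|---|---|---|
| IP likelier | Related | Related |
| Equally likely | Related | Neither comparison is met |
| Other cause likelier | Related | Not related (one OR limb suffices) |

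**Row 1.** The two standards agree.

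**Row 3.** This is a direct conflict. The event meets the opening sentence of Related and a sufficient limb of Not related.

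**Row 2.** This depends on how the sentences under Related are read. If all must hold, the event fails the last one and meets no limb of Not related, so it fits neither category. If the opening sentence governs, it is Related. The text does not choose.

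**Direction.** Applying the comparison can only remove events from Related. It cannot add any, because an event for which the vaccine is the likelier explanation already has a reasonable possibility.

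**Consistency with the SAP.** SAP 6.3.2 describes an AR as an AE related to the injection, so AR and Related are meant to coincide. Under 7.4.1 a row 3 event is an AR; under the last limb of Not related it is not related.

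**Size.** Let R be the number of events related under the reasonable-possibility standard, and f the share of them that the comparison removes. The count becomes R × (1 − f), a relative loss of f. The documents give neither R nor f. Assuming f between 10% and 50% returns a loss of 10% to 50%, which merely restates the assumption. For participant counts the loss need not equal f, since a participant leaves the related row only if every one of their related events is reclassified.

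**Scope.**
- Solicited ARs are all treated as related (7.4.3). Reactions reported verbally but not captured in the eDiary (7.3.1), or starting after Day 7 (note to Table 5), are handled as AEs outside that rule and so are exposed to the conflict.
- In-study AE reporting does not depend on causality (7.4.9, 7.4.10). SAEs and AESIs go to the sponsor within 24 hours whatever their relatedness (7.4.5, 7.4.11).
- The primary safety endpoints (protocol Tables 1 and 2; SAP 3.1.1 and 3.2.1) count events irrespective of causality.

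**The case against.** The strongest reply is that the opening sentences govern. They are exact complements, so the scheme is exhaustive at that level and the rest is elaboration. The sentences under Related are not joined by AND, so an equally likely event, which meets no limb of Not related, falls naturally under Related. That reading is available and largely answers the tie. It does not answer the case where another cause is likelier, because a limb of Not related is then met outright.

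A second reply is that the gloss on reasonable possibility in 7.4.1 is limited to investigational new drug reporting. That is correct, but the conflict does not need the gloss: both thresholds stand within 7.4.9.

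A third is that the consequences are narrow. Treatment-related rows are supporting summaries without confidence intervals, suspected myocarditis and pericarditis are adjudicated independently, and no hypotheses are tested. The wording is the same for every arm and Part A assessors are blinded, so nothing in the documents points to distorted comparisons between arms. All of this stands and limits the point.

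A reader might infer that treatment-related AEs are in fact undercounted, perhaps by a stated percentage. The documents do not support that. The loss arises only where investigators apply the comparison, and no rate is given.

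**Conclusion.** The conflict is real and sits inside one section. An unsolicited AE or SAE with a reasonable possibility of IP causation but a likelier alternative satisfies text in both categories, and neither document says which prevails. The place of an equally likely event is unclear, though it can be read as Related; a reader who concludes that it certainly fits neither category goes further than the text.

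To the extent that investigators apply the comparative text, treatment-related counts and relatedness-dependent reporting of SAEs after participation ends can only fall relative to the protocol's reasonable-possibility standard. The size cannot be computed. The direction rests on one assumption: that reasonable possibility is a lower bar than being the likelier cause, as its use in 7.4.1 and 7.4.11 implies. Solicited ARs, total AE and SAE counts, in-study reporting and the primary safety endpoints are not affected.

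**What to change.** Reconcile 7.4.9 with 7.4.1 and 7.4.11. State that the reasonable-possibility sentence decides the category. Then either delete the two comparative clauses, or keep alternative causes only as a factor the investigator weighs in reaching that judgement. The second option preserves guidance on alternative causes that deletion would remove. Either way the categories become complementary and the tie is settled. Carry the rule into the eCRF completion instructions.

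The cost is a wording amendment with the approvals that requires, and somewhat more events labelled related. There is also a transition issue. The synopsis estimates first enrolment on 29-Nov-2021 and the current amendment is dated 31 Jan 2022, so Part A events may already have been classified under the existing text. If so, record the date of the change, and either review the earlier assessments or note the difference in the CSR, so that two standards are not pooled without comment. Sample size, visits and participant procedures do not change.

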#### **7.4.10. Reporting Adverse Events**

The investigator is responsible for reporting all AEs that are observed or reported during the study, regardless of their relationship to IP or their clinical significance. If there is any doubt as to whether a clinical observation is an AE, the event should be reported.

All unsolicited AEs reported or observed during the study will be recorded on the AE page of the eCRF. Information to be collected includes type of event, time of onset, investigator-specified assessment of severity (impact on activities of daily living) and relationship to IP, time of

resolution of the event, seriousness, as well as any required treatment or evaluations, and outcome. The unsolicited AEs resulting from concurrent illnesses, reactions to concurrent illnesses, reactions to concurrent medications, or progression of disease states must also be reported. All AEs will be followed until they are resolved or stable or judged by the investigator to be not clinically significant. The Medical Dictionary for Regulatory Activities (MedDRA) will be used to code all unsolicited AEs.

Any medical condition that is present at the time of screening but does not deteriorate should not be reported as an unsolicited AE. However, if it deteriorates at any time during the study, it should be recorded as an unsolicited AE.

#### **7.4.11. Reporting SAEs**

Prompt notification by the investigator to the Sponsor of an SAE is essential so that legal obligations and ethical responsibilities toward the safety of participants and the safety of a study intervention under clinical investigation are met.

Any AE considered serious by the investigator or that meets SAE criteria ([Section 7.4.2](#)) must be reported to the Sponsor immediately (within 24 hours of becoming aware of the SAE) via the EDC system. The investigator will assess whether there is a reasonable possibility that the IP caused the SAE. The Sponsor will be responsible for notifying the relevant regulatory authorities of any SAE as outlined in 21 US CFR Parts 312 and 320. The investigator is responsible for notifying the institutional review board (IRB) directly.

If the eCRF is unavailable at the time of the SAE, the following contact information is to be used for SAE reporting:

- SAE Mailbox: Safety\[contact]
- SAE Hotline (USA and Canada): [contact]
- SAE Fax Line (USA and Canada): [contact]

Regulatory reporting requirements for SAEs are described in [Section 7.4.15](#).

The investigator and any qualified designees are responsible for detecting, documenting, and recording events that meet the definition of an AE, including SAEs, and remain responsible for following up AEs that are serious, considered related to IP or study procedures, or that caused the participant to discontinue the study.

Any SAE occurring after the EoS and considered to be caused by the study vaccine must be reported to the Sponsor.

#### **7.4.12. Time Period and Frequency for Collecting AE, AESI, and SAE Information**

Medical occurrences that begin before IP administration but after obtaining informed consent will be recorded in the Medical History/Current Medical Conditions section of the eCRF and not in the AE section; however, if the condition worsens at any time during the study, it will be recorded and reported as an AE.

Adverse events may be collected as follows:

- Observing the participant
- Receiving an unsolicited complaint from the participant
- Questioning the participant in an unbiased and nonleading manner

Solicited AEs will be collected from the day of injection through 6 days after vaccination. Other (unsolicited) AEs will be collected from the day of injection through 28 days after vaccination.

Serious AEs (including AESIs) will be collected from the start of IP administration until the last day of study participation.

All SAEs and AESIs will be recorded and reported to the Sponsor or designee immediately and under no circumstance should this exceed 24 hours of becoming aware of the event via the EDC system. If a site receives a report of a new SAE or AESI from a study participant or receives updated data on a previously reported SAE or AESI and the eCRF has been taken offline, then the site can report this information on a paper SAE or AESI form using the SAE Mailbox, the SAE Hotline, or the SAE Fax line ([Section 7.4.11](#)).

An abnormal value or result from a clinical or laboratory evaluation can also indicate an AE if it is determined by the investigator to be clinically significant (eg, leads to study drug discontinuation or meets any serious criteria). If this is the case, it must be recorded in the source document and as an AE on the appropriate AE form(s). The evaluation that produced the value or result should be repeated until that value or result returns to normal or is stabilized and the participant's safety is not at risk.

Investigators are not obligated to actively seek AEs or SAEs after EoS participation. However, if the investigator learns of any SAE (including a death) at any time after a participant has withdrawn from or completed the study, and the investigator considers the event to be reasonably related to the IP or study participation, the investigator must promptly notify the Sponsor.

#### **7.4.13. Method of Detecting AEs and SAEs**

Electronic diaries have specifically been designed for this study by the Sponsor. The diaries will include prelisted AEs (solicited ARs) and intensity scales; they will also include blank space for

the recording of information on other AEs (unsolicited AEs) and concomitant medications/vaccinations.

The investigator is responsible for the documentation of AEs regardless of treatment group or suspected causal relationship to IP. For all AEs, the investigator must pursue and obtain information adequate to determine the outcome of the AE and to assess whether the AE meets the criteria for classification as an SAE requiring immediate notification to the Sponsor or its designated representative.

Care will be taken not to introduce bias when detecting AEs and/or SAEs. Open-ended and nonleading verbal questioning of the participant is the preferred method to inquire about AE occurrences.

#### **7.4.14. Follow-up of AEs and SAEs**

After the initial AE/SAE report, the investigator is required to proactively follow each participant at subsequent visits and contacts.

All AEs and SAEs will be treated as medically appropriate and followed until resolution, stabilization, the event is otherwise explained, or the participant is LTFU, as defined in [Section 6.3](#).

#### **7.4.15. Regulatory Reporting Requirements for SAEs**

- Prompt notification by the investigator to the Sponsor of an SAE is essential so that legal obligations and ethical responsibilities toward the safety of participants and the safety of a study intervention under clinical investigation are met.
- The Sponsor has a legal responsibility to notify both the local regulatory authority and other regulatory agencies about the safety of a study intervention under clinical investigation. The Sponsor will comply with country-specific regulatory requirements relating to safety reporting to the regulatory authority, IRBs, and investigators.
- Investigator safety reports must be prepared for suspected unexpected serious ARs according to local regulatory requirements and Sponsor policy and forwarded to investigators as necessary.
- An investigator who receives an investigator safety report describing an SAE or other specific safety information (eg, summary or listing of SAEs) from the Sponsor will review and then file it along with the IB and will notify the IRB, if appropriate according to local requirements.

## **7.5. Safety Monitoring**

Safety monitoring for this study will include an unblinded DSMB.

Blinded safety monitoring for this study will include study team members, inclusive of, at a minimum, the Sponsor medical monitor, Sponsor safety physician (from Pharmacovigilance), and CRO medical monitor. The study team will conduct ongoing safety reviews during the study and will be responsible to monitor for safety concerns during the study as described in the Safety Management Plan.

An independent CEAC that includes pediatric and adult cardiologists will review suspected cases of myocarditis and pericarditis to determine if they meet CDC criteria of “probable” or “confirmed” events, and to assess severity.

## **7.6. Treatment of Overdose**

As the study treatment is to be administered by a healthcare professional, it is unlikely that an overdose will occur. Dose deviations will be tracked as protocol deviations ([Section 10.2.8](#)).

## **7.7. Pharmacokinetics**

Pharmacokinetic parameters are not evaluated in this study.

## **7.8. Pharmacodynamics**

Pharmacodynamic parameters are not evaluated in this study.

## **7.9. Biomarkers**

Immunogenicity assessments are described in [Section 7.1](#). Biomarkers are not evaluated in this study.

## **7.10. Health Economics**

Health economics are not evaluated in this study.

